**3.4.9 Modified Intent-to-Treat Subjects**

A Modified Intent-to-Treat (MITT) Subject is an ITT Subject who receives any energy delivery for PVI with the randomized endocardial ablation catheter at an Index / Rescheduled Index Procedure.

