### 3.4.12 Per Protocol Subjects

A Per Protocol (PP) Subject is a Safety or ITT Subject without major protocol deviations that would affect the completeness, accuracy and reliability of the study data. Major protocol deviations that exclude subjects from a PP Population are the following:

- Failure to meet any of the following study entry criteria:
  - Arrhythmia different than PAF (Inclusion Criterion 1)
  - Prior cardiovascular procedures, implants or conditions (Exclusion Criteria 3 and 4)
  - Medical conditions (Exclusion Criterion 11)
- Failure to receive the randomized ablation treatment for PVI as specified in this protocol (**Section 5.2 or Section 5.3**)
- Receipt of a prohibited study drug (amiodarone, except intra-procedurally to control an arrhythmia )
- In addition, the data of Severe COVID-19 Subjects will be censored beginning on the Onset Date of infection.

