#### 6.3.2 Acute Procedural Failure

The absence of Acute Procedural Success, including the use of any non-randomized energy modality for PVI.

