#### 7.4 Primary Effectiveness Endpoint

**Treatment Success:** The primary effectiveness endpoint is Treatment Success in MITT Subjects, defined as:

1. **Acute Procedural Success (Section 6.3.1) AND**
2. **Chronic Success**, defined as freedom from:
  - a. At the Index / Rescheduled Index Procedure: Use of a non-randomized treatment modality for PVI
  - b. After the Blanking Period:
    - i. Occurrence of any Detectable AF, AFL or AT (**Section 6.3.11**) (excluding CTI-dependent flutter confirmed by EP study)
    - ii. Any cardioversion for AF, AFL or AT (excluding for CTI-dependent flutter)
    - iii. Use of any Type I or Type III antiarrhythmic medication for the treatment of AF, AFL or AT
  - c. At any time:
    - i. Re-ablation for AF, AFL or AT (other than for CTI-dependent flutter)
    - ii. Use of amiodarone, except intra-procedurally to control an arrhythmia

Endpoint status will be assessed through the Month 12 Assessment (Day 360  $\pm$  30).

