STATISTICAL ANALYSIS PLAN

Document: CS0935 Rev C, ADVENT Statistical Analysis Plan

Study Title: The FARAPULSE ADVENT Trial: A Prospective Randomized Pivotal Trial of the FARAPULSE Endocardial Ablation System Compared with Standard of Care Ablation in Patients with Paroxysmal Atrial Fibrillation

Study Device: FARAPULSE Endocardial Ablation System

Sponsor: FARAPULSE, Inc.

Author: [REDACTED]

Date: 12 Oct 2021

Signature: _____ Date: _____

Analysis Summary

Study Title: The FARAPULSE ADVENT Trial: A Prospective Randomized Pivotal Trial of the FARAPULSE Endocardial Ablation System Compared with Standard of Care Ablation in Patients with Paroxysmal Atrial Fibrillation

Primary Objective: The objective of this pivotal study is to provide valid scientific evidence that endocardial ablation using the FARAPULSE Endocardial Ablation System is both safe and effective for treating drug-resistant paroxysmal atrial fibrillation (PAF).

The following endpoint definitions from the ADVENT Protocol are provided for convenience. Any discrepancy with the ADVENT Protocol is inadvertent unless specifically identified as a deliberate change (or clarification) of the protocol's definition.

Primary Effectiveness Endpoint

The primary effectiveness endpoint is Treatment Success, a composite defined in the Protocol as:

1. Acute Procedural Success AND
2. Chronic Success, defined as freedom from:
 - a. At the Index/Rescheduled Index Procedure: The use of a non-randomized treatment modality for pulmonary vein isolation (PVI)
 - b. After the Blanking Period:
 - i. The occurrence of any Detectable AF, AFL or AT (excluding CTI-dependent flutter confirmed by EP study)
 - ii. Any cardioversion for AF, AFL or AT (excluding for CTI-dependent flutter)
 - iii. The use of any Type I or Type III anti-arrhythmic medication for the treatment of AF, AFL or AT
 - c. At any time:
 - i. Re-ablation for AF/AFL/AT (other than for CTI-dependent flutter)
 - ii. Use of amiodarone

Endpoint status will be assessed through the Month 12 Assessment (Day 360 ± 30). The incidence of Treatment Success will be assessed for non-inferiority.

Secondary Effectiveness Endpoint:

The secondary effectiveness endpoint is the same as the primary effectiveness endpoint but will be tested for superiority rather than non-inferiority.

Additional Effectiveness Endpoints

1. Acute Procedural Success
2. Acute Vein Success
3. Chronic Success
4. Chronic Success Allowing Re-ablation
5. Chronic Success Allowing AADs

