4.1.12 Per Protocol Subjects

Per Protocol (PP) Subjects are all Subjects without major protocol deviations that would affect the completeness, accuracy and reliability of the study data. Major protocol deviations¹ that exclude subjects from the PP Population are the following:

- Failure to meet any of the following study entry criteria:
 - Arrhythmia different than PAF (Inclusion Criterion 1)
 - Prior cardiovascular procedures, implants or conditions (Exclusion Criteria 3, 4)
 - Medical conditions (Exclusion Criterion 11)
- Failure to receive the randomized ablation treatment for PVI as specified in Protocol Section 5.2 and Protocol Section 5.3.
- Receipt of a prohibited study drug (amiodarone)
- In addition, the data of Severe COVID-19 Subjects will be censored beginning on the Onset Date of infection.

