5.1 Primary Effectiveness Endpoint (Protocol Section 7.4)

The primary effectiveness endpoint is Treatment Success, which is a composite of the following criteria:

1. Acute Procedural Success AND
2. Chronic Success, defined as freedom from:
 - a. At the Index/Rescheduled Index Procedure: The use of a non-randomized treatment modality for PVI
 - b. After the Blanking Period:
 - i. The occurrence of any Detectable AF, AFL or AT (Section 6.3.10) (excluding CTI-dependent flutter confirmed by EP study)
 - ii. Any cardioversion for AF, AFL or AT (excluding for CTI-dependent flutter)
 - iii. The use of any Type I or Type III anti-arrhythmic medication for the treatment of AF, AFL or AT
 - c. At any time:
 - iv. Re-ablation for AF/AFL/AT (other than for CTI-dependent flutter)
 - v. Use of amiodarone

Endpoint status will be assessed through 360 ± 30 days.

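### The Per Protocol effectiveness analysis removes subjects for an event that is itself a Treatment Failure (amiodarone outside the procedure), and probably also subjects who crossed over; it should be reported with and without them

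*Protocol*

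**What the plan says.** **PP exclusions.** Protocol Section 3.4.12 lists the deviations that remove a subject from PP. Two matter here: "Receipt of a prohibited study drug (amiodarone, except intra-procedurally to control an arrhythmia" and "Failure to receive the randomized ablation treatment for PVI as specified in this protocol".

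**Endpoint.** Protocol Section 7.4 counts as a failure, at any time, "Use of amiodarone, except intra-procedurally to control an arrhythmia"; Section 5.9 states the same rule. Section 7.4 also counts a non-randomized PVI modality at the index procedure as a failure, and Section 6.3.2 defines Acute Procedural Failure as "The absence of Acute Procedural Success, including the use of any non-randomized energy modality for PVI".

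**MITT.** Section 3.4.9 requires only that the subject "receives any energy delivery for PVI with the randomized endocardial ablation catheter". A subject can therefore be in MITT and still have crossed over.

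**Role of PP.** Protocol Sections 9.6 and 9.10 make PP the sensitivity analysis for effectiveness non-inferiority and superiority. SAP Section 6 defines study success by the two primary non-inferiority tests, and the plan sets no pass criterion for PP.

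**SAP wording.** The SAP leaves out the intra-procedural exception in three places: the Analysis Summary ("ii. Use of amiodarone"), Section 5.1 ("v. Use of amiodarone") and the PP exclusion in Section 4.1.12 ("Receipt of a prohibited study drug (amiodarone", with the bracket closed at once).

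**The concern.** A PP exclusion should select on how the subject was treated, not on the outcome. Here one exclusion is an outcome: everyone removed for non-procedural amiodarone has already failed the endpoint. PP then differs from MITT partly because known failures were deleted, and agreement or disagreement between the two is harder to interpret.

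The rule also treats like cases differently. Protocol Section 6.3.4 lists amiodarone among the Class III drugs. A subject given sotalol for a recurrence after blanking is a failure who stays in PP; a subject given amiodarone for the same recurrence disappears from PP, recurrence included. Section 5.9 adds that Class I/III use for subject welfare is not a protocol deviation, while Section 3.4.12 lists amiodarone as a major one.

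Treating physicians are not blinded (Section 5.7), so equal removal in the two arms cannot be taken for granted. At stake is the reading of a sensitivity analysis.

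**Working it through.** **1. The plan's own figure.** SAP Section 11.2 gives 172 per arm (344 in total) for 0.65 v 0.65, margin 0.15, one-sided 0.05 and 90% power. The Farrington-Manning formula returns 172. The unpooled formula gives (1.645 + 1.282)² × 2 × 0.65 × 0.35 / 0.15² = 173.2, so 174. The figure stands, and this point does not touch it, because these subjects count as failures in MITT.

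**2. How far each exclusion overlaps with failure.**
- Amiodarone: the exclusion and the endpoint failure carry the same exception, so the overlap is complete.
- Randomized PVI not received as specified: an MITT subject who crossed over at the index procedure is a failure. Other departures from Section 5.2 can still end in success, so the overlap is partial.

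**3. Effect on the success rate.** If a share a of an arm is removed and all of them are failures, success goes from p to p/(1-a).

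**4. Size for non-inferiority.** Inputs from the SAP: null 0.50 v 0.65 (Section 14), Beta(0.5, 0.5) priors and threshold 0.956 (Section 9.1). Assumptions: 225 per arm before removal (half of the 450 in Protocol Section 4.4), complete data, no interim looks, and every removal rate. The last column is the exact binomial probability of exceeding 0.956 if that threshold were applied to PP.

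| Removed, Pulsed Field / Thermal | PP n | Success | Difference (points) | Pass probability |
|---|---|---|---|---|
| none | 225 / 225 | 50.0% v 65.0% | -15.0 | 0.047 |
| 1% / 1% | 223 / 223 | 50.5% v 65.7% | -15.2 | 0.041 |
| 2% / 2% | 220 / 220 | 51.0% v 66.3% | -15.3 | 0.038 |
| 1% / 2% | 223 / 220 | 50.5% v 66.3% | -15.8 | 0.031 |
| 2% / 1% | 220 / 223 | 51.0% v 65.7% | -14.6 | 0.053 |
| 5% / 2% | 214 / 220 | 52.6% v 66.3% | -13.7 | 0.078 |
| 2% / 5% | 220 / 214 | 51.0% v 68.4% | -17.4 | 0.012 |

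At 175 and 375 per arm, 2%/1% gives 0.053 and 0.054, and 1%/2% gives 0.031 and 0.029 (no removal: 0.043 and 0.045).

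**5. Size for superiority.** At 0.65 in both arms, threshold 0.977 and 225 per arm: 0.023 with no removal, 0.033 at 2%/1% (+0.7 points) and 0.016 at 1%/2% (-0.7 points).

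**6. One borderline dataset.** With 128/225 v 146/225 the difference is -8.0 points and the posterior probability of non-inferiority is 0.939.
- Drop five Pulsed Field failures: 128/220 v 146/225, -6.7 points, 0.966.
- Drop five Thermal failures: 128/225 v 146/220, -9.5 points, 0.889.
- Drop five from each arm: -8.2 points, 0.933.

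**7. SAP wording, if coded literally in MITT.** If a share b of an arm had intra-procedural amiodarone, and those subjects would otherwise succeed at the arm's rate, success becomes p(1-b). At the null with 225 per arm, against 0.047: 1%/1% gives 0.050; 2%/2% gives 0.053; 1%/2% gives 0.066 (0.495 - 0.637 = -14.2 points); 2%/1% gives 0.0395 (0.490 - 0.6435 = -15.35 points). These rates of use are also assumed.

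**The case against.** **PP is meant to exclude such subjects.** A PP population leaves out those who took a prohibited drug or did not get the assigned treatment, and MITT already counts them as failures, so the plan reports both views. This is largely fair, and it is why the as-defined PP analysis should stay. It does not explain why amiodarone failures leave PP while failures on other Class I/III drugs remain.

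**The crossover exclusion is not explicit.** Section 3.4.12 does not mention partial crossover or touch-up, and Section 5.2 asks that ablation be attempted in every relevant vein. This stands: removal is the natural reading, since PVI is to be done with the randomized devices, but it is not certain.

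**The effect is small and decides nothing.** This stands too. The 2%/1% result of 0.053 lies inside the SAP's own simulation interval of 0.0457 to 0.0543 (Section 14). Larger shifts need imbalances for which the documents give little support: acute success was 40/40, 71/71 and 10/10 in the earlier studies (Protocol Sections 1.4.1 to 1.4.3), and amiodarone within 3 months of consent is an exclusion (Section 3.3.2). Those facts do not bear directly on the Thermal arm or on amiodarone given after a recurrence.

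**Stronger readings that a reader might infer.**
- That the SAP sets a different primary endpoint. It does not: it calls unflagged differences from the protocol inadvertent (Analysis Summary, Sections 4 and 5), and Section 9.1 tests Treatment Success as defined in Protocol Section 7.4. The results in step 7 arise only if those statements are ignored.
- That SAP Section 16.3, which counts some extra ablations as failures, shows a conflicting standard. It does not: Protocol Section 5.2 permits those ablations and says that they are not Treatment Failures, so the cases are not comparable.
- That the PP rule favours Pulsed Field. Nothing in the documents shows which arm would lose more subjects.

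**Conclusion.** The point holds as a minor weakness of a sensitivity analysis. The amiodarone overlap is certain from the text; the crossover overlap is probable but not stated. Removing definitional failures raises PP success in each arm and moves the difference in either direction when removal is unequal. At 1-2% removal and 225 per arm, the null pass probability stays between 0.031 and 0.053, against 0.047. It reaches 0.078 or falls to 0.012 only at imbalances such as 5%/2% or 2%/5%.

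All of these rates are assumed, and the calculation ignores missing data, interim looks and other PP exclusions. The threshold is applied to PP for illustration only. The principal MITT analysis, sample size, error control and study success do not change. The SAP's amiodarone wording is a reconciliation item that the SAP's own clauses already settle in favour of the protocol definition.

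**What to change.** 1. Report the PP effectiveness analysis in two versions: as now defined, and with MITT subjects kept as Treatment Failures when their only PP deviation is itself an endpoint component (amiodarone outside the intra-procedural exception, or non-randomized PVI after some randomized energy).
2. State in Protocol Section 3.4.12 and SAP Section 4.1.12 whether partial crossover is a PP exclusion.
3. Tabulate PP exclusions by arm and reason. Protocol Section 9.3 asks for numbers excluded, but not in this form.
4. Before analysis, reconcile the amiodarone text in the SAP Analysis Summary and Sections 4.1.12 and 5.1 with the Protocol Summary and Protocol Sections 3.4.12 and 7.4.

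The cost is some wording, one extra PP analysis and one table, with no new data and no change to the primary test. The second PP version lies closer to MITT and says less about subjects treated exactly as assigned; keeping the first version beside it avoids that loss.

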### 3.5 Subject Disposition Chart

**Figure 5 Subject Disposition Chart**

**MITT** = modified intent-to-treat, **ITT** = intent-to-treat

 Major protocol deviations also include such events as failure of informed consent, confidentiality violations and actions that may affect the subject's rights, safety or well-being. These, while serious, generally do not impact the validity of data collected and so are not part of the per protocol exclusions for outcome assessment.

### **3.6 Subject Informed Consent**

All subjects must provide documented informed consent using the Institutional Review Board (IRB)-approved informed consent form (ICF) / electronic informed consent form (eICF) before undergoing any study-related procedures. If electronic consent is utilized it will conform to the FDA Guidance Document “Use of Electronic Informed Consent, Questions and Answers”, dated December 2016 (or subsequent revised versions as applicable).

Since it may become necessary during this study to access study-specific protected healthcare information from remote clinical sites, the ICF / eICF will include this permission in the consent process.

Subjects cannot be asked to sign the ICF / eICF until the study has been fully approved by the institution’s IRB and the Sponsor or their clinical research organization (CRO) representative has received and reviewed the IRB-approved ICF / eICF. Subjects who meet the general eligibility criteria will be asked to sign an ICF / eICF as approved by the relevant regulatory authorities before any study-specific tests or procedures are performed.

The Investigator or a designated member of their staff should communicate with the subject to obtain written informed consent. As far as possible, non-technical language shall be used that is understandable to the subject. The background of the proposed study and the benefits and risks of the procedures and study should be explained. The subject should be provided with ample time to read the ICF / eICF and discuss it with their family and physician. The subject shall be informed that their participation in the clinical investigation is confidential. The ICF / eICF must be read and understood by the subject and the subject’s questions answered. The ICF / eICF must be signed and dated by both the subject and physician / designee overseeing informed consent prior to subject enrollment and before the subject undergoes any study-related procedures. All subjects are to receive copies of their signed and dated ICF / eICF. A copy of the approved ICF / eICF along with a copy of each subject’s signed ICF / eICF will be maintained by the Investigator in a designated clinical study administrative file or electronic record system. Subjects may not be consented after receiving any medication that might alter their ability to comprehend the consent form (e.g., sedatives, narcotics, etc.). Study personnel should explain that even if a subject agrees to participate in the study and signs the ICF / eICF, the subject may not be eligible to participate if the subject fails to meet the screening criteria.

Written informed consent must be obtained prior to performing any protocol-driven tests or any procedures that are not standard of care for a percutaneous ablation procedure that the subject is scheduled to undergo. Once written consent has been obtained, the subject will be entered on a Screening Log, which will be maintained at each site. All subjects who provide written informed consent will be entered into the Screening Log regardless of whether they are enrolled in the study.

### **3.7 Subject Enrollment**

Subjects that meet all the eligibility criteria and are deemed suitable by the Investigator will be invited to participate in the study.

When initial screening indicates that the subject will likely meet the inclusion and exclusion requirements and agrees to participate in the study, formal written informed consent using the current IRB-approved ICF will be obtained.

Provisional subject enrollment occurs when the ICF has been signed. Enrollment is confirmed when all study eligibility requirements are determined to have been met.

If one or more of the required pre-enrollment assessments – including cardiac CT/MRI, transthoracic echocardiography (TTE), laboratory tests and ECG – have not been obtained prior to signing the ICF, then the enrollment is considered provisional until that assessment has been obtained and the criteria met.

Regardless of the sequence of ICF completion and pre-procedural enrollment assessments, if study eligibility criteria are not met, the subject is a Screen Failure and is not enrolled.

Study eligibility criteria are determined at the time of study entry. In the instance that information received after an Index Procedure / Rescheduled Index Procedure reveals that an inclusion or exclusion criterion – determined prior to the Index Procedure / Rescheduled Index Procedure to have been met – is found to have been incorrectly assessed, this does not change the enrolled status of the subject, who remains in the study.

Each Enrolled Subject will be assigned a unique study identification code to protect each subject's confidential health information. The unique study identification code will not include date of birth or subject's first and last initials and will be used to link study data and other study information to the subject in lieu of the subject name. The Subject Name Log will be used to link the unique study identity code to the subject and will be maintained at the site. This log will remain confidential and will not be provided to the Sponsor but only used for reference when monitoring at the study site.

### **3.8 Subject Randomization**

Subjects excluding Roll-In Subjects – who are determined by the Investigator at the time of assessment to have met all pre-randomization inclusion and exclusion criteria, who have signed an ICF and who are scheduled for the Index Procedure – will be randomized. The study staff will confirm documented inclusion / exclusion success prior to requesting randomization.

### **3.9 Subject Completion or Exit**

When a subject completes the study at the Month 12 Assessment, exceeds 390 days of follow-up without a Month 12 Assessment, or exits prior to such completion, they will return to standard medical care and a study termination/exit CRF will be completed, including the reason for exit.

Subjects may voluntarily withdraw from the study at any time for any reason. The Investigator may terminate the subject without subject consent at any time to protect the subject's rights, safety or welfare. Subjects leaving the study prior to completion will continue to receive appropriate medical care without prejudice.

## **4. Study Summary and Schedule**

### **4.1 Study Objective and Hypothesis**

The primary objective of this pivotal study is to determine whether there is valid scientific evidence that endocardial ablation using the FARAPULSE Pulsed Field Ablation System is both safe and effective for treating drug-resistant symptomatic PAF.

The primary clinical hypotheses of this pivotal study are that PVI created by the FARAPULSE Pulsed Field Ablation System is not inferior in safety and effectiveness to treatment with approved catheter ablation technologies (force-sensing radiofrequency or cryoballoon ablation) in the treatment of drug-resistant symptomatic PAF.

### **4.2 Study Overview**

This is a prospective, adaptive, multi-center, randomized safety and effectiveness pivotal study comparing the FARAPULSE Pulsed Field Ablation System with standard of care ablation with force-sensing RF catheters and cryoballoon catheters indicated for the treatment of PAF. Subjects will undergo ablation for PVI with the randomized treatment and if indicated CTI ablation using an RF catheter. Subjects will be followed at 7 days (telephonic), 30 days, 90 days, 6 months and 12 months for AEs, recurrence of arrhythmia after a 90-day Blanking Period and other relevant outcome measures.

